#### 7.0 Study Procedures

All of the below mentioned procedures are being conducted for purposes of the research. Please see Table 1 for information regarding which visit to the laboratory these procedures will take place.

• Facilities: Visit 2 will take place at the Counsilman-Billingsley Aquatics Center, a 44,651 square foot aquatics center used by Indiana's varsity swimming and diving programs. It contains an eight-lane Olympic-sized pool spanning 30,512 square feet with depth ranging from seven to eight feet to allow for greater speed. A photo depicting the Counsilman-Billingsley Aquatics Center is below (Figure 3).

## Figure 2: Photo of the Counsilman-Billingsley Aquatics Center where Visit 2 will take place.

Visits 3 and 4 will take place in the swim flume (Endless Pool). This pool works like a "swimming treadmill," pushing water from the front (near side in Figure 4) to the back at various flow rates to simulate various swimming speeds. A standard pulley is affixed to the back of the flume to add a tethered load to the swimmer, like changing the "grade" on a treadmill. This is a familiar training environment for high-level competitive swimmers. A photo depicting the swim flume in the IUB School of Public Health is below (Figure 4).

Figure 3: Photo of the swim flume where Visits 3 and 4 will take place.

- Height: Body height will be measured using a stadiometer.
- Weight: Weight will be measured using a scale.
- Heart rate: Resting heart rate will be obtained by taking a radial pulse for 15 seconds during the screening procedure. Exercising and pre-exercise heart rate will be continuously recorded using a specialized waterproof swimming heart rate monitor (Cardio Swim HR monitor; Freelap, Switzerland).
- Urine specific gravity: Urine specific gravity will be measured via refractometry.
- Blood pressure: Blood pressure will be measured using standard brachial artery manual auscultation techniques.
- Health history questionnaire: Participants will complete a health history questionnaire to ensure they meet the inclusion and exclusion criteria.

- Health history update questionnaire: Upon each visit to the laboratory participants will complete the heath history update questionnaire to ensure no changes in their health history has occurred.
- Pulmonary function: Pulmonary function will be examined using procedures described by the American Thoracic Society. Following 10 min seated rest, participants will be fitted with a previously disinfected non-rebreathing mouthpiece. Following 30 s of normal breathing the participants will be instructed to take a maximal inhalation followed by a maximal forced exhalation. This very large, very fast breath will be repeated three times. From this test peak expiratory flow rate (PEFR), forced vital capacity (FVC), forced expiratory volume in one second (FEV1), and the maximal expiratory flow at 50% vital capacity (MEF50) will be measured. These tests will be used to determine if the participants classify as having normal pulmonary function (Barreiro and Perillo, 2004).
- Venous blood sample: Venous blood will be drawn by a trained researcher from an antecubital vein using standard aseptic techniques, as defined by the World Health Organization. Each blood draw will be ~10 mL (Experimental Trials) or 15 mL (Selection Exercise Protocol) total. Measurements include:
  - Complete blood count: Samples will be collected into EDTA-coated Vacutainer tubes (Becton Dickinson, Franklin Lakes, NJ). The samples will be immediately stored on ice and transported to a local medical facility (Student Health Center, Indiana University, Bloomington, Indiana) that will perform a complete blood count using an automated hematology analyzer (SX-1000i; Sysmex, Kobe, Hyogo, Japan). The complete blood count will assess hemoglobin, hematocrit, white blood cell count, red blood cell count, mean corpuscular volume, mean corpuscular hemoglobin concentration, platelets, neutrophil percentage, lymphocyte percentage, neutrophil number, lymphocyte number, monocyte number, eosinophil number, basophil number, red cell distribution width standard deviation, red cell distribution width coefficient of variation, and mean platelet volume.
  - Plasma volume correction: In order to account for loss of plasma volume during exercise, all plasma-derived post-exercise measures will be corrected via the methods of Dill and Costill (1974). First, post-exercise blood volume (BVA) is determined via the equation:

$$BV_A = BV_B \times \frac{Hb_B}{Hb_A}$$

where  $Hb_B$  is the pre-exercise hemoglobin concentration,  $BV_B$  is the preexercise blood volume and is 100 for the purpose of this equation,  $Hb_A$  is the post-exercise hemoglobin concentration. Whole blood histamine concentration will then be corrected based on the differences in the blood volume pre- and post-exercise ( $\Delta BV_A$ -BVB%). BVA is then used to determine post-exercise red cell volume (CVA) via the equation:

$$CV_A = BV_A \times Hct_A$$

where  $Hct_A$  is the post-exercise hematocrit value.  $CV_A$  is then used to determined post-exercise plasma volume ( $PV_A$ ) via the equation:

$$PV_A = BV_A - CV_A$$

Concentration of plasma-derived biomarkers will then be corrected based on the differences in plasma volume pre- and post-exercise ( $\Delta PV_A - PV_B\%$ ). Hemoglobin and hematocrit will be assessed in triplicate from a venous blood sample.

- Plasma IL-1β: Samples will be collected into EDTA-coated Vacutainer tubes (Becton Dickinson, Franklin Lakes, NJ). The samples will be immediately stored on ice and transported to the laboratory where they will be centrifuged at 4°C at 1,300 *g* for 10 minutes and 2000 *g* for 15 minutes (model X-22R; Beckman, St. Louis, MO). Two-hundred microliters of plasma will be aliquoted into 0.5 mL cryogenic storage vials (CryoKING®, Biologix, Jinan, Shandong, China) and stored immediately at −80°C. Samples will be later diluted accordingly and analyzed in duplicate using a commercially-available enzyme-linked immunoassay (ELISA) kit (Invitrogen #BMS224HS; Thermo Fisher Scientific, Waltham, MA, USA) with detection by spectrophotometry (Powerwave XS™ Spectrophotometer, Bio-Tek Instruments, Winooski, VT). Based on a previous study, it is expected that plasma IL-1β in this cohort will be 1-15 pg·mL (Mucci et al., 2000). The sensitivity of this assay is 0.05 pg·mL and the range is 0.16-10.0 pg·mL.
- Plasma IL-8: Samples will be collected, processed, and stored as previous. Samples will be later analyzed in duplicate with a commercially-available ELISA kit (Invitrogen #KHC0084; Thermo Fisher Scientific, Waltham, MA, USA) with detection as previous. Based on a previous study, it is expected that plasma IL-8 will be 0-10 pg·mL (Mucci et al., 2000). The sensitivity of this assay is <100 fg·mL and the range is 0.39-25 pg·mL.
- Plasma histamine: Samples will be collected as previous. The samples will be immediately stored on ice and transported to the laboratory where they will be centrifuged at 4°C at 900 *g* for 15 minutes (model X-22R; Beckman, St. Louis, MO). Samples will be analyzed in duplicate with a commercially-available ELISA kit (AB213975; Abcam, Cambridge, United Kingdom) with detection as previous. Based on a previous study, it is expected that plasma histamine will be 1-6 ng·mL (Mucci et al., 2000). The sensitivity of this assay is 0.03 ng·mL and the range is 0.098-25 ng·mL.

- Whole blood histamine: Samples will be collected into heparinized Vacutainer tubes (Becton Dickinson, Franklin Lakes, NJ). Fifty microliters of whole blood will be pipetted into 950 µL of distilled water and stored at -80°C in 1 mL vials (Eppendorf Tubes®; Eppendorf, Hamburg, Germany) until analysis. The diluted blood will be fully thawed and frozen twice more to ensure cell lysis. For analysis, thawed samples will be centrifuged as previous and the supernatant will be analyzed using a commercially-available ELISA kit and detected as previous. Based on a previous study, it is expected that whole blood histamine will be between 600-1400 ng·mL (Mucci et al., 2000). The sensitivity of this assay is 0.03 ng·mL and the range is 0.098-25 ng·mL.
- Histamine release: Histamine release (%H) will be calculated via the equation:

$$\%H = \frac{PH}{WH} \times 100$$

where PH is the plasma histamine concentration and WH is the whole blood histamine concentration.

- Selection exercise test: This test will take place in a standard 25-yard swimming pool (Counsilman-Billingsley Aquatics Center). Following a standardized 1000 yds (914.4 m) warm-up, an intense exercise protocol will be used to elicit release of inflammatory markers. At his or her fastest sustainable pace, each swimmer will complete 6 x 100 yards (91.4 meters), 6 x 50 yds (45.7 meters), and 6 x 25 yards (22.9 meters) of freestyle swimming with 10 seconds of rest between each of the 18 total bouts. This is a common exercise paradigm that is typically completed by collegiate and professional swimmers during their training season. Blood draws for assessment of inflammatory markers will be completed 1 hour prior to commencement of the warm-up and immediately following completion of the last intense exercise bout.
- Peripheral capillary oxyhemoglobin saturation (SPO2): This measurement will take place during the experimental trials in the swimming flume in the IU Human Performance Laboratory. A pulse oximetry sensor (Covidien/Medtronic, Dublin, Ireland) will be placed on the subject's forehead after application of a topical vasodilator (Finalgon; Boehringer Ingelheim, Ingelheim am Rhein, Germany). Though the probe has its own adhesive, an adhesive bandage patch (Tegaderm; 3M, Saint Paul, MN) will be placed over the top to further secure and waterproof the probe below a standard swimming cap. SPO2 will be monitored through a standard bedside pulse oximetry unit (Nellcor N600x; Covidien/Medtronic, Dublin, Ireland) outputting an analog signal to a customized A/D board (Hector Engineering, Ellettsville, IN) and recorded at a 1 Hz sampling frequency by a customized computer program (DasyLab 13.0; Measurement Computing Corporation, Norton, MA).
- Indirect calorimetry: During the experimental trials in the swimming flume, resting and exercise metabolic (VO2 and VCO2) and ventilatory (VE, fB, and VT) variables will be

measured breath-by-breath using a portable metabolic computer (K5; Cosmed, Rome, Italy) suspended above the Endless Pool and adapted for swimming exercise (Aquatrainer, Cosmed, Rome, Italy). This portable system has been determined to be valid and reliable while using breath-by-breath mode (Guidetti et al., 2018) and will be calibrated according to the manufacturer's instructions prior to each test. The swimmer will breathe through a customized two-way, nonrebreathing snorkel mouthpiece (Hans Rudolph, Shawnee, KS).

- Graded exercise test: After a self-determined warm-up and a rest period of at least 2 minutes, a progressive maximal exercise test will be performed in a specially constructed, customized variable water flow pool (Endless Pools, Aston, PA, USA), with subjects swimming against a flow rate of approximately 1.5 m·s for men and 1.31 m·s for women tethered to a pulley with a 1.2 and 1 kg mass, respectively. After two minutes, the tethered mass will be increased by 0.2 kg every two minutes until each subject reaches volitional exhaustion. Metabolic and ventilatory variables and SPO2 will be measured as described below. Subjects' heart rates during the tests will be continuously recorded (Cardio Swim HR Monitor; Freelap, Switzerland). VO2MAX will be considered as the maximal value attained during the test, provided at least two of three criteria are met, which will include an RER of greater than 1.05, achievement of 90% of age-predicted maximal heart rate, and an increase in VO2 of less than 0.15 L/min over the previous workload. Plasma histamine, whole blood histamine, and histamine release will be measured before and after this test as previous.
- Constant load tests: Following the maximum exercise test, subjects will perform constant load swimming exercise at approximately 70 and 85% of subjects' previously recorded HRMAX during that session. The tethered mass used to elicit the workloads will be estimated during the first 20-minute rest period by performing a linear regression between HR and tethered mass to approximate the tethered mass that would elicit 70 and 85% of maximum HR. Subjects will swim for 5 minutes. Metabolic and ventilatory variables and SPO2 will be measured as described below. Plasma histamine, whole blood histamine, and histamine release will be measured following these tests as previous.
- Drug administration An opaque sugar-free gelatin capsule (Capsuline, Dania Beach, Florida, USA) will be administered 60 minutes prior to testing and will either be empty (placebo) or contain CH (10 mg; Zyrtec®; Johnson & Johnson, New Brunswick, NJ, USA) according to the visit condition.

Timeline of procedures:

Screening Visit (Visit 1): Once participants arrive at the laboratory, an investigator will
obtain written informed consent after all procedures and study risks are fully explained
and all questions answered. Participants will then complete a pre-exercise health
screening questionnaire and a health history questionnaire. The PI and/or approved
study team member will administer these questionnaires/assessments. These
individuals can fully explain any technical terms and answer any inquiries related to

the questionnaires. Participants will also have their resting heart rate and blood pressure, height, and weight in a private room. They will then complete a pulmonary function test. This visit will take approximately 1 h. If the participant is female, they will be asked to self-identify when their last menses (period) occurred. To prevent sex differences caused by fluctuations in hormone across the menstrual cycle, experimental visits (2-5) for female participants will only be tested during the first 7 days following menstruation when estrogen and progesterone hormones are at their lowest levels.

- Selection Exercise Protocol (Visit 2): Participants will arrive to the Counsilman-Billingsley Aquatics Center after abstaining from allergy medication for 48 hours, intense exercise for 24 hours, caffeine and alcohol for 12 hours, and food for 2 hours. They will complete the health history update questionnaire to ensure there have been no changes in their health history. Following a standardized 1000 yds (914.4 m) warmup, an intense exercise protocol will be used to elicit release of inflammatory markers. At his or her fastest sustainable pace, each swimmer will complete 6 x 100 yards (91.4 meters), 6 x 50 yds (45.7 meters), and 6 x 25 yards (22.9 meters) of freestyle swimming with 10 seconds of rest between each of the 18 total bouts. A venous blood draw will be completed 30 minutes prior to commencement of the warm-up and immediately following completion of the last intense exercise bout.
- Experimental Trials (visits 3 and 4): Prior to all testing sessions, participants will be asked to abstain from allergy medication for 48 hours, intense exercise for 24 hours, caffeine and alcohol for 12 hours, and food for 2 hours. Prior to the sessions 3-4, participants will also be asked to consume a similar diet the night before and day of each testing session. Women participants will be asked to self-identify when their last menses occurred. In order to prevent sex differences caused by fluctuations in hormone across the menstrual cycle, women participants will only be tested during the first 7 days following menstruation (when estrogen and progesterone hormones are at their lowest levels) for sessions 2-4 (Allen et al., 2016). Apart from receiving a placebo (PL) or drug treatment (CH) prior to exercise, participants will perform identical protocols on each visit to the laboratory. Participants will report to the lab and consume either a placebo or CH pill, followed by a health history update questionnaire and their resting pulmonary function will be measured. Participants will then complete a self-selected warm-up that will be standardized across the two testing sessions, followed by instrumentation. The exercise protocol beings with a progressive swimming test to maximum aerobic capacity (VO2max) in a swimming flume, followed by two constant load work bouts at approximately 70 and 85% of the previously recorded HRmax while peripheral capillary oxyhemoglobin saturation ( $S_pO_2$ ) is continuously monitored. Participants will receive a 20-min break between each work bout. Drug treatments will be assigned in a double-blind, randomized crossover fashion such that each participant receives each treatment. Concentrations of plasma histamine, whole blood histamine, and histamine release will be assessed from a venous blood draw one hour prior to commencement of the aerobic capacity test, and immediately following the aerobic capacity test and each of the two constant load bouts.

**8.0 Study Calendar** The following procedures will be undertaken during the visits.

Table 1: Description of Stud	v Procedures that will take	place on each visit to the laboratory.
	y i roccuures that will take	

STUDY PROCEDURES	Screening (Visit 1)	Selection Exercise Test (Visit 2)	Experimental Trials – Randomized Crossover (Visits 3-4)	
			Placebo	Cetirizine HCI
Height	Х		Х	Х
Weight	Х		Х	Х
Heart rate	Х		Х	Х
Urine specific gravity		Х	Х	Х
Blood pressure	Х			
Health history questionnaire	Х			
Health history update questionnaire		X	Х	Х
Pulmonary function	Х		Х	Х
Complete blood count		X		
Plasma IL-1β		X		
Plasma IL-8		X		
Plasma histamine		Х	Х	Х
Whole blood histamine		Х	Х	Х
Histamine release		Х	Х	Х
Selection exercise test		X		
Peripheral capillary oxyhemoglobin saturation			Х	Х
Indirect calorimetry			Х	Х
Graded exercise test			Х	Х
Constant load tests			Х	Х
Placebo pill			Х	
Cetirizine HCI pill				Х

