Those selected for further study will visit the Human Performance Laboratory on two occasions separated by at least 48 hours and no more than 60 days. Apart from receiving a placebo (PL) or drug treatment (cetirizine HCl, CH) prior to exercise, participants will perform identical protocols on each visit to the laboratory. Participants will report to the lab and consume either a placebo or CH pill, followed by a health history update questionnaire and their resting pulmonary function will be measured. Participants will then complete a self-selected warm-up that will be standardized across all testing sessions, followed by instrumentation. The exercise protocol beings with a progressive swimming test to maximum aerobic capacity ( $\dot{V}O_{2max}$ ) in a swimming flume, followed by two constant load work bouts at approximately 70 and 85% of the previously recorded HRmax while peripheral capillary oxyhemoglobin saturation (SpO2) is continuously monitored. Participants will receive a 20-min break between each work bout. Drug treatments will be assigned in a double-blind, randomized crossover fashion such that each participant receives each treatment. Concentrations of plasma histamine, whole blood histamine, and histamine release will be assessed from pre- and post-exercise blood samples.

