#### 6.0 Enrollment/Randomization

We plan to recruit up to 30 participants for this project to ensure that at least 24 participants will complete the first two visits of the study.

Participants will be recruited from the Indiana University varsity swim team and the associated professional training group. Indiana University is home to a NCAA Division I swim team that is perennially among the nation's top-10 for both men and women. Participants will be recruited from this group of over 50 swimmers using a standard email script.

[figure not shown]
Potential participants will be given the basic information about the study and schedule an appointment for screening if they indicate that they would be interested in participating. Participants will be provided a with detailed description of study procedures prior to study enrollment. Participants will be asked to read the consent form at this time and be encouraged to ask any questions. Participants can then: 1) sign the consent form; 2) take it home for further consideration; or 3) decide not to participate. Participants will be screened once written informed consent has been given.

Experimental trials 3 and 4 will be completed in a double-blinded randomized crossover design. The randomization order will be determined using a customized program (Excel; Microsoft Corporation, Redmond, WA, USA). Subjects will be randomized using the randomization list by order of enrollment in the study by a researcher listed on the IRB personnel. This researcher will also be responsible for drug administration but will otherwise not participate in any data collection or analyses.

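### The placebo capsule is empty and the active one is filled, so a swimmer who takes both may notice a difference; matching them with inert filler is a cheap protection for effort-dependent outcomes

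*Combined protocol and SAP*

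**What the plan says.** The drug administration paragraph of 7.0 Study Procedures uses the same shell for both conditions, "An opaque sugar-free gelatin capsule", which "will either be empty (placebo) or contain CH". It mentions no filler, no weight matching and no check on the blind.

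The blinding claim is explicit. Section 5.0 states: "Drug treatments will be assigned in a double-blind, randomized crossover fashion such that each participant receives each treatment". Section 6.0 states: "Experimental trials 3 and 4 will be completed in a double-blinded randomized crossover design". The visit timeline in 7.0 repeats the claim and describes the intake: "Participants will report to the lab and consume either a placebo or CH pill". Section 6.0 also assigns drug administration to a researcher who takes no other part in data collection or analysis.

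On the exercise side, 7.0 raises the tethered mass in the graded test "until each subject reaches volitional exhaustion". The two constant-load bouts then use about 70 and 85% of the "previously recorded HR MAX during that session". Aim 2 (2.1) compares nadir SpO2 between placebo and cetirizine at 70, 85 and 100%. Section 3.1 lists both SpO2 and VO2 as primary outcomes.

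**The concern.** An opaque shell hides what the contents look like. It does not hide that one capsule is empty. In a parallel-group trial a participant would have nothing to compare with; here each swimmer swallows one of each. Section 6.0 recruits from one varsity team and its associated professional group, so swimmers can also exchange impressions.

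An instrument-read endpoint is usually robust to a participant's beliefs. It is less so here, because the swimmer produces the exercise that drives the reading. If effort follows the guessed treatment, and the guess is right more often than not, the resulting shift moves with treatment and is counted as a treatment effect. The carry-over check in 12.0 examines visit order, so it would not pick this up. A capsule mismatch cannot be repaired once data are collected.

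**Working it through.** The plan gives no figure for blinding, so there is none to reproduce. The check sets the relevant statements side by side and then uses Table 2 for scale.

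**1. Do the capsules differ?** Same shell, one empty and one containing product. A weight difference follows whatever form the contents take. Its size, and whether a person could detect it, are not given.

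**2. Who is protected?**
- *Staff who collect or analyse data:* largely protected, because a separate researcher gives the capsule (6.0), unless a swimmer tells them.
- *The swimmer:* protected only by opacity.

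**3. Can a guess reach the outcomes?**
- *100%:* yes, directly. The test ends when the swimmer stops. VO2 depends on effort in the same way.
- *70 and 85%:* yes, indirectly. If HRmax differs by *d* beats/min between visits, the target heart rates differ by 0.70*d* and 0.85*d*, and the tethered mass is read off that session's regression of heart rate on mass.
- *Acceptance criteria:* VO2max is accepted when two of three criteria are met. An RER above 1.05 plus 90% of age-predicted maximal heart rate is enough without a plateau. Two tests by one swimmer can therefore both qualify with different effort.

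**4. How sensitive is saturation to intensity?** Inputs are from Table 2 (12.0), at 70, 80, 90 and 100% of VO2max.

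| | 70 | 80 | 90 | 100 |
|---|---|---|---|---|
| Placebo | 93.7 | 93.4 | 93.0 | 89.8 |
| Diphenhydramine | 96.5 | 96.2 | 95.8 | 94.2 |
| Difference | 2.8 | 2.8 | 2.8 | 4.4 |

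Fall in the placebo row per 10-point step:
- 70 to 80: 93.7 − 93.4 = 0.3, which is 0.3/2.8 = 11% of the planning difference.
- 80 to 90: 93.4 − 93.0 = 0.4, which is 0.4/2.8 = 14%.
- 90 to 100: 93.0 − 89.8 = 3.2, which is 3.2/4.4 = 73%.

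The submaximal range is nearly flat. Any material effect on SpO2 would be at 100%.

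**5. Illustration at 100%.** Assume that the last step is linear (3.2/10 = 0.32 points per percentage point of VO2max) and that peak intensity differs between visits by 3 to 5 percentage points. The shift within a swimmer is then 3 × 0.32 = 0.96 to 5 × 0.32 = 1.6 points, or 0.96/4.4 = 22% to 1.6/4.4 = 36% of the planning difference. If only a fraction *p* of swimmers behave this way, the mean shift is *p* times that. With 4 of 12, for example, it is 0.32 to 0.53 points (7 to 12%). The 3-to-5-point range and the 4 of 12 are assumptions; the documents supply neither.

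**The case against.** The strongest reply has five parts.

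**The cue may be weak.** One might infer that a loose tablet rattles and that swimmers handle the capsules and compare them. The text says only that the capsule contains CH and is consumed. It does not say whether the contents are intact, loose or packed. Section 5.0 separates the visits by at least 48 hours and up to 60 days, so the capsules are never side by side, and the first one has no comparator. This stands: detectability is unknown. The weight difference itself remains.

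**The direction is unclear.** One might infer bias in favour of cetirizine. A swimmer who tries harder on the believed-active visit would, if anything, desaturate more, which works against the Aim 2 hypothesis. A false positive needs less effort on that visit, and the documents give no reason to expect it. This also stands.

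**Not all intensities are equally exposed.** One might infer that all three are compromised. Table 2 does not support that, as the working shows.

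**Effort is partly monitored.** Heart rate, VO2 and ventilation are recorded, and 12.0 applies the treatment-by-intensity models to the dependent variables of interest. A treatment difference in VO2 could therefore come to light. It would be wrong to say that nothing planned could show a problem. But such a difference could come from the drug or from expectation, and without treatment guesses the trial has no direct data on the blind.

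**Filler cannot secure the blind.** Section 9.0 lists drowsiness and dry mouth among the side effects. True, and this is a reason to collect guesses as well as to match the capsules.

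**Conclusion.** The concern holds as a risk. The plan specifies capsules that differ in weight while claiming a double blind in a crossover, and neither the opaque shell nor the separate administrator addresses what the swimmer may notice. Effort linked to a guessed treatment can affect VO2 and nadir SpO2, mainly at 100%; the effect at 70 and 85% is likely small.

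The documents do not show that unblinding will occur, and neither the size nor the direction of any bias can be derived from them. The Table 2 figures give scale only. They are ear-oximetry data from male runners at set percentages of VO2max with a different antihistamine, whereas 7.0 sets the submaximal swimming loads from heart rate. A reader should not conclude that Aim 2 is invalid or that a positive result would be spurious. This is a cheap improvement that removes an avoidable alternative explanation.

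**What to change.** 1. In the drug administration paragraph of 7.0, replace the empty placebo with a capsule containing inert filler. Use the same filler in the active capsule as needed, so that the two match in weight and feel. State this, and state that the active product is unchanged.
2. At the end of Visit 4, before allocation is revealed, ask each swimmer and the tester which visit they believe was active, and report the guesses alongside Aim 2. With 12 swimmers this is descriptive. If every guess were a coin toss, 9 or more correct has probability (220 + 66 + 12 + 1)/4096 = 0.073, and 10 or more has (66 + 12 + 1)/4096 = 0.019. Correct guesses may also reflect side effects or a drug effect that the swimmer felt, so they do not isolate the capsule as the cause.
3. In 12.0, add a sentence that the between-visit comparison of peak heart rate and VO2 will be read as a partial check on equal effort.

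Cost: filler, a little preparation time, one question and a few sentences. The filler must be compatible with the intolerances and additive allergies in the exclusion criteria (4.2). The remaining weakness is that side effects such as drowsiness could still unblind some swimmers.
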